5.4 Strategies for Recruitment and Retention

We will recruit 54 total participants from ages 9 months – 17 years of age from the inpatient pediatric units at Tisch Hospital or ODA clinic. Our sample size calculation determined 22 participants in each arm (drug vs placebo) of the study to see a 60% reduction in MRSA colonization at a power level of 80%. We anticipated a 20% drop out rate based on prior studies of retention and therefore an additional 5 patients were added per arm of study.

Patients admitted to the general inpatient or pediatric intensive care units at NYU Langone Medical Center Tisch hospital will be recruited if they reside in a pre-defined zip code that is identified as an Orthodox predominant neighborhood. A daily report will be generated for patients admitted from these zip codes and sent to the Infection Prevention and Control team (specifically the PI [name]).

Recruitment will be conducted by either the PI and co-investigator or study team members. The children will not necessarily be under the care of the PI or co-investigators, or some instances they may be if they are admitted with an infection that requires a Pediatric Infectious Diseases consult and the PI and co-investigator are the physicians who are covering the service. Otherwise, when patients from the defined zip-codes are admitted, a report that captures these patients will be created and sent to the PI and co-investigator. The study team will approach the parent/guardian explaining how they were identified for the potential study. It will be explained that the research team is not aware of their current reason for admission and will not access their Epic chart for this reason. Once permission is obtained from the

CONFIDENTIAL

This material is the property of the NYU School of Medicine and Langone Medical Center. Do not disclose or use except as authorized in writing by the study sponsor
Interventional Template Version: 28 APR 2017

parent/guardian, then the child will be approached to discuss the study. Participants will also be recruited at the ODA clinic (Park Ave location) In Brooklyn. These participants will be referred for screening by clinic members, pediatricians in the community, or by word of mouth.

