5.6 Total Number of Participants and Sites

The total number of participants enrolled will be 54 subjects. 27 in each of the two arms of the study.

Recruitment will end when approximately 54 participants are enrolled and have completed the study protocol. It is expected that approximately 54 participants will be enrolled in order to produce 44 evaluable participants as we estimate a 20% drop out rate. The participants will be recruited at NYULMC Tisch Hospital or ODA clinic in Brooklyn.

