10.2 Statistical Hypotheses

Primary endpoint

The percent change in nasal/rectal colonization of MRSA from baseline to 1 week after completion of decolonization protocol with retapamulin compared to placebo

Null hypothesis: There will be no difference in reduction of nasal/rectal colonization of MRSA from baseline to 1 week after completion of decolonization protocol between retapamulin compared to placebo

Alternative hypothesis: There will be a 45% difference in reduction in nasal/rectal colonization of MRSA from baseline to 1 week after completion of decolonization protocol with retapamulin compared to placebo

Secondary endpoint

The percent change in nasal/rectal colonization of MRSA from baseline to 4 weeks after completion of decolonization protocol with retapamulin compared to placebo

Null hypothesis: There will be no difference in reduction of nasal/rectal colonization of MRSA from baseline to 4 weeks after completion of decolonization protocol between retapamulin compared to placebo

CONFIDENTIAL

This material is the property of the NYU School of Medicine and Langone Medical Center. Do not disclose or use except as authorized in writing by the study sponsor

Alternative hypothesis: There will be a 45% difference in reduction in nasal/rectal colonization of MRSA from baseline to 4 weeks after completion of decolonization protocol with retapamulin compared to placebo

This analysis will be a superiority trial.

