10.4.2 Analysis of the Primary Efficacy Endpoint(s)

To assess the primary dichotomous endpoint, the change in nasal/rectal colonization of MRSA from baseline to 1 week after completion of decolonization protocol with retapamulin compared to placebo, we will use a fisher exact (non-parametric) to evaluate for significant difference in colonization after 1 week between the two groups. We will provide the difference in decolonization rates with an odd ratio, 95% confidence interval and p-value. Participants will be selected to treatment group at random, therefore baseline characteristics should not significantly differ. However if the two treatment groups have covariates that are significantly different, we will consider a logistic regression to adjust for the difference

CONFIDENTIAL

This material is the property of the NYU School of Medicine and Langone Medical Center. Do not disclose or use except as authorized in writing by the study sponsor
Interventional Template Version: 28 APR 2017

in population. Before we analyze with a logistic regression, we will test for normality to assure that all apriori statistical assumptions are met.

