10.5 Sample Size

The table below presents ranges of the required sample size based on the primary trial endpoint of the change in nasal/rectal colonization of MRSA from baseline to 1 week after completion of decolonization protocol at approximately 80% power. It provides a range of sample size depending on the potential effectiveness of retapamulin.

Computed N Per Group		
Proportion Diff	Actual Power	N Per Group
0.30	0.809	42
0.35	0.801	32
0.40	0.807	26
0.45	0.822	22
0.50	0.811	18
0.55	0.802	15
0.60	0.808	13
0.65	0.841	12

The sample size calculation was based on prior literature indicating a 60% decolonization rate; a 45% difference in decolonization between groups (60% retapamulin vs 15% placebo/spontaneous decolonization) at 80% power. This is taken into account a 15% spontaneous decolonization rate as reported in the literature. Power calculation analyses were performed in SAS 9.3 (SAS Institute, Cary NC) using fisher's exact conditional test for two proportions (Walters normal approximation with exact conditional distribution). A 20% lost to follow up was estimated and added to the final sample size number. Therefore, the total number of participants enrolled will be 54 subjects – 27 in each of the two arms of the study.

It is estimated that 0.8-6% of the general population is colonized with MRSA. Colonization in persons with previous infection is estimated to be 20%. We suspect this percent is higher in the particular population we aim to study as it is a high risk population for MRSA colonization and infection. Therefore we estimate screening 500 participants to meet the sample size goal of our study.

CONFIDENTIAL

This material is the property of the NYU School of Medicine and Langone Medical Center. Do not disclose or use except as authorized in writing by the study sponsor

We will use fisher exact test at alpha .05 to determine a significant difference between treatment groups (retapamulin vs placebo). Participants who withdraw before the 1 week primary endpoint will be excluded from analysis as the primary end point will not be recorded.

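### Fisher's exact test is valid and meets the 80% target, but naming Boschloo's exact test as primary would add about 3.6 points of power on average with the same children and the same 5% limit

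*Combined protocol and SAP*

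**What the plan says.** Section 10.5 sets the test and level: "We will use fisher exact test at alpha .05 to determine a significant difference between treatment groups (retapamulin vs placebo". Section 10.4.2 repeats the choice for the primary endpoint: "we will use a fisher exact (non-parametric) to evaluate for significant difference in colonization after 1 week between the two groups". It promises an odds ratio, a 95% confidence interval and a p-value. Section 10.4.3 does the same for week 4.

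The sample size rests on "a 45% difference in decolonization between groups (60% retapamulin vs 15% placebo/spontaneous decolonization) at 80% power". The method is given as "fisher's exact conditional test for two proportions (Walters normal approximation with exact conditional distribution", and the table prints power 0.822 with 22 per group. Section 5.4 confirms the number ("Our sample size calculation determined 22 participants in each arm (drug vs placebo) of the study"), and section 5.6 gives the total ("approximately 54 participants will be enrolled in order to produce 44 evaluable participants as we estimate a 20% drop out rate"). Section 10.5 also excludes from the analysis children who withdraw before the week 1 endpoint.

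Sidedness is not stated. No section mentions that Fisher's test is conservative or considers an unconditional exact test.

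**The concern.** Fisher's test conditions on the total number of children cleared. The design sets how many children are assigned to each arm, but not that total. In small samples the conditional test can take only a few p-values, so its true type I error falls well short of 0.05 and power is lost.

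Boschloo's test uses Fisher's p-value as its statistic and finds the largest cut-off that keeps the unconditional error at or below 0.05. It rejects whenever Fisher does, and in some further tables. What is at stake is a modest increase in the risk of a false-negative trial, in a population where section 10.5 expects to screen 500 to reach the target.

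**Working it through.** **Inputs.** Rates 0.60 and 0.15, alpha 0.05, 22 evaluable per arm, 27 per arm enrolled, 20% loss (sections 5.4, 5.6, 10.5). Two-sided testing is an assumption. It fits the null in 10.2 ("Null hypothesis: There will be no difference in reduction of nasal/rectal colonization of MRSA from baseline to 1 week after completion of decolonization protocol"), and it reproduces the plan's table.

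**Step 1: the plan's figure.** Walters approximation, n per arm:

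power = Φ( √(2n) × [arcsin√(p2 − 1/(2n)) − arcsin√(p1 + 1/(2n))] − 1.96 )

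With n = 22: √44 × (0.8630 − 0.4286) = 2.881; 2.881 − 1.960 = 0.921; Φ(0.921) = 0.822. The plan prints 0.822. All eight rows of the table reproduce to the third decimal.

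**Step 2: exact values at 22/22.** Enumerate all 23 × 23 outcomes of two independent binomials. Power is the probability of the rejection region at (0.60, 0.15). Maximum type I error is its largest probability over a grid of common rates.

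- Fisher, two-sided: power 0.8273; maximum error 0.0244, which is 0.0244/0.05 = 49% of the allowance.
- Boschloo: power 0.8945; maximum error 0.0497; equivalent Fisher p cut-off 0.0946.
- Gain: 0.8945 − 0.8273 = 0.067, or 6.7 points.

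**Step 3: other analysed arm sizes.** Early withdrawals are excluded, so equal arms cannot be assumed. Expected evaluable per arm is 27 × 0.80 = 21.6. Same rates and level:

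| Retapamulin/placebo | Fisher max. error | Fisher power | Boschloo power | Gain (points) |
|---|---|---|---|---|
| 20/20 | 0.025 | 0.797 | 0.851 | 5.4 |
| 21/21 | 0.023 | 0.799 | 0.874 | 7.5 |
| 22/22 | 0.024 | 0.827 | 0.895 | 6.7 |
| 21/22 | 0.036 | 0.859 | 0.894 | 3.5 |
| 22/21 | 0.036 | 0.844 | 0.882 | 3.8 |
| 21/23 | 0.036 | 0.844 | 0.902 | 5.8 |
| 20/24 | 0.034 | 0.851 | 0.898 | 4.8 |
| 27/27 | 0.026 | 0.914 | 0.941 | 2.7 |

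These pairs give roughly 3 to 7 points. A few others give less: enumerating every pair from 20 to 24 per arm, the smallest gain was 1.0 point (23/24) and the largest 7.5 (21/21).

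**Step 4: average over the plan's own loss.** Weight each pair of arm sizes by two independent Binomial(27, 0.80) probabilities. Mean Fisher power is about 0.849 and mean Boschloo power 0.884, a gain of about 3.6 points. Keeping the rarest small arms in the average moves Fisher to 0.848 and leaves the gain at 3.6. Mean Fisher maximum error is about 0.034. Equal arms occur about 14% of the time, and Fisher's maximum error is below 0.025 in about 7%.

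**Step 5: dependence on the rates (22/22).** For 0.60 against 0.20: 0.691 with Fisher, 0.791 with Boschloo. For 0.50 against 0.15: 0.608 and 0.716.

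**The case against.** The strongest reply is that nothing in the plan is wrong. Fisher's test is named consistently, it is the test used to size the trial, and the sample size already pays for its conservatism. That stands, and it makes this an improvement rather than a correction.

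Second, Fisher's test can be defended as the randomisation test of no effect in any child, under which the total cleared is fixed and no sampling model is needed. Boschloo's guarantee needs two independent binomials, in children recruited through admissions, referral and word of mouth during an outbreak. This is a fair reservation. The plan's own power calculation rests on the same two-binomial model, so the change adds no assumption to the design, though it does bring that assumption into the test.

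Third, all the extra power comes from tables where Fisher does not reject. At 22/22 there are 14 such tables favouring retapamulin, with Fisher p from 0.055 to 0.095. An example is 11/22 cleared against 4/22. In each, the exact conditional 95% interval for the odds ratio includes 1, so the interval promised in 10.4.2 would contradict the new test. This stands and has to be dealt with in the fix.

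Fourth, section 4.1 calls both week 1 and week 4 primary outcome measures, while 4.2 makes week 4 secondary and 10.4.9 declares multiplicity not applicable. At 22/22 Fisher's slack happens to hold two tests to 2 × 0.0244 = 0.049 by Bonferroni. With Boschloo that bound is 2 × 0.0497 = 0.099. The change is therefore sound only if week 1 is the sole primary endpoint.

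Finally, section 10.1 defers full detail to a stand-alone SAP. That is a natural place to make the change, but 10.4.2 and 10.5 already name the test and must agree with it.

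**Conclusion.** The point holds as a cheap gain in efficiency. On the plan's own rates and loss, naming Boschloo's test would raise average power by about 3.6 points, and by 6.7 points if exactly 22 are analysed in each arm. This rests on two-sided 0.05, 60% against 15%, independent binomial outcomes and independent 20% loss in each arm.

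A reader might infer three stronger things, and the documents support none of them:

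- That the trial is underpowered or its test invalid. The printed 0.822 reproduces, and exact power at 22 per arm is 0.827.
- That Fisher uses less than half of its allowed error and the gain is about 7 points. That describes equal arms of 21 or 22. Section 10.5 excludes early withdrawals and section 10.6.1 describes no blocking, so such arms will be uncommon.
- That enrolment could be cut. With placebo clearance of 20% instead of 15%, Boschloo's power at 22/22 is 0.791, below the target.

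**What to change.** Before unblinding, amend 10.4.2 and 10.5, and the stand-alone SAP to match:

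1. Name Boschloo's exact unconditional test, two-sided 0.05, computed at the realised arm sizes, as the primary test. State the sidedness and the software routine.
2. Report an exact unconditional 95% confidence interval for the difference in decolonization rates, with its construction named. Check that it agrees with the test across the possible tables. Label any conditional odds-ratio interval as supplementary.
3. Report Fisher's p-value as a sensitivity result, and say in advance that the Boschloo result governs where the two differ.
4. State that week 1 is the sole primary endpoint, with week 4 secondary or tested only after week 1 succeeds, and bring section 4.1 into line.
5. Leave the sample size unchanged. The Fisher calculation then serves as a conservative basis.

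The cost is a few lines of text and possibly a routine outside the named SAS 9.3. The downside is a less familiar test and some borderline results (Fisher p roughly 0.05 to 0.095 at 22/22) where readers will see two tests disagree. No child, visit or procedure is added.

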5.7.2 Handling of Participant Withdrawals or Termination

For patients who have withdrawn or terminated from the study, follow up telephone calls will be conducted to assess for side effects. One phone call two weeks after the patient has been declared

CONFIDENTIAL

This material is the property of the NYU School of Medicine and Langone Medical Center. Do not disclose or use except as authorized in writing by the study sponsor
Interventional Template Version: 28 APR 2017

withdrawn or terminated will be conducted. For patients who remain in the study, but discontinue the study agent, they will be asked to complete the follow up questionnaire when they present for study visits to assess for adverse reactions or side effects. Adverse events from the drug are local at the site of application and should subside with the discontinuation of the product. Therefore, long term follow up for adverse events is deemed unnecessary.

A participant will be stated as lost to follow-up (and therefore withdrawn/terminated) if: they have missed all three study visits, the study team has attempted weekly phone calls to parent/guardian for three weeks without answer or success of having the participant return for study visit.

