6.1.9 Duration of Therapy

Each ointment will be applied for five consecutive days. The five days is necessary for an 'evaluable' participant

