10.1 Statistical and Analytical Plans (SAP)

There will be a formal Statistical and Analytical Plan (SAP). Partial details as outlined in the below sections, with full SAP created by study biostatistician being part of a stand-alone document. Key elements of the analysis plan are described below.

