10.3 Analysis Datasets

This will be a triple-blinded randomized Intent to Treat (ITT) clinical trial to assess the effectiveness of retapamulin in children colonized with MRSA under the age of 18 from a pre-specified community in Brooklyn. Participants living in the following zip codes will be eligible: 11024, 11205, 11206, 11211, 11213, 11214, 11218, 11219, 11225, 11230, 11249. Neither the treatment team nor the subject will know the treatment assignments. The outcome will be a dichotomous variable (1 = Yes, patient's swab negative for MRSA, 0 = No, Patient's swab positive for MRSA). We will analyze additional co-variables collected on the data collection form such as age, gender, history of MRSA infections, history of chronic medical conditions/chronic skin conditions, etc. (see Data Collection Form in appendix uploaded into study-related documents).

Information from the data collection form will be entered into an Access database designed for this study to provide a readily electronic version dataset to analyze. The following variables will be included: Assigned group (blinded treatment arm, A/B), age, gender, side effects, application day 1 (Y/N), application day 2 (Y/N), application day 3 (Y/N), application day 4 (Y/N), application day 5 (Y/N), environmental clean (Y/N), history of medical conditions or chronic skin conditions, history of MRSA, history of MRSA in family, recent or concomitant antibiotic use, prior retapamulin use etc. Variables related to safety will also be recorded in the database.

In addition to the ITT analysis, we will conduct a per-protocol analysis of those who completed 4 or 5 days of treatment and analyze similar to the ITT analysis.

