10.4 Description of Statistical Methods

10.4.1 General Approach

The design of the study is a randomized, double-blind, placebo-controlled clinical trial. Schematic of Study design on page 2 of this document illustrates further.

This will be a double-blinded randomized Intent to Treat (ITT) clinical trial to assess the effectiveness of retapamulin in children colonized with MRSA under the age of 18 from a pre-specified community in Brooklyn. The outcome will be a dichotomous variable (1 = Yes, patient's swab negative for MRSA, 0 = No, Patient's swab positive for MRSA). We will analyze additional co-variables collected on the data collection form such as age, gender, history of MRSA infections, history of chronic medical conditions/chronic skin conditions, etc. (see Data Collection Form in appendix uploaded into study-related documents). These will be presented as descriptive statistics between Retapamulin and Placebo groups and assessed for potential statistical differences between the groups. Chi-square will be used for dichotomous variables and a T-test will be used for continuous variables (if normally distributed otherwise Mann-Whitney).

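### The primary analysis is labelled Intent to Treat, but section 10.5 drops randomized children who withdraw before the 1-week swab, and the supplied text plans no analysis of all randomized children

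*Combined protocol and SAP*

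**What the plan says.** All references are to the combined protocol and SAP.

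- Section 10.3, Analysis Datasets: "This will be a triple-blinded randomized Intent to Treat (ITT) clinical trial to assess the effectiveness of retapamulin". It continues: "In addition to the ITT analysis, we will conduct a per-protocol analysis of those who completed 4 or 5 days of treatment".
- Section 10.4.1, General Approach, repeats the label: "This will be a double-blinded randomized Intent to Treat (ITT) clinical trial".
- Section 10.5, Sample Size, last sentence: "Participants who withdraw before the 1 week primary endpoint will be excluded from analysis as the primary end point will not be recorded".
- Section 5.6 sizes the trial on that basis: "approximately 54 participants will be enrolled in order to produce 44 evaluable participants as we estimate a 20% drop out rate".
- Section 6.1.9 uses the same word differently: "The five days is necessary for an 'evaluable' participant".
- Section 10.1 announces a fuller plan, "with full SAP created by study biostatistician being part of a stand-alone document". That document was not supplied.

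The outcome in 10.3 and 10.4.1 is binary, 1 for a negative swab and 0 for a positive one, with no code for a missing swab. Section 7.3.2 places randomization at Visit 1 (Day 0). Section 7.3.3.1 places the endpoint culture at Visit 2 (Day 14 ± 5, so Day 9 to 19). Section 7.3.5 says a swab will be attempted when a participant withdraws.

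**The concern.** An ITT analysis compares everyone randomized, in the arm assigned. Section 10.5 removes some randomized children because of something that happens after randomization. The comparison reported as ITT would therefore rest on children with a Visit 2 result, and the only second analysis, per-protocol, narrows the set further.

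The exclusion does harm when loss is related to outcome in a way that distorts the comparison between arms. Equal numbers lost in the two arms do not rule this out, because the children lost from one arm may differ in outcome from those lost from the other. The documents give no basis for predicting the direction. What is at stake is a reader trusting an ITT label that does not apply, with no planned analysis in the supplied text to show how far the conclusion depends on the missing children.

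**Working it through.** **1. The plan's own figure.** Inputs from 10.5: 60% v 15% decolonization, alpha 0.05, Fisher's exact test, Walters approximation. Sidedness is not stated; the two-sided form reproduces the table. With n per arm,

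power = Φ(√(2n) × [arcsin√(p1 − 1/(2n)) − arcsin√(p2 + 1/(2n))] − 1.96).

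For n = 22: √44 × (0.8630 − 0.4286) = 2.881, and Φ(2.881 − 1.960) = 0.822, the tabulated value. Full enumeration of Fisher's test gives 0.827. The sample size is not in dispute.

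**2. How many children are involved.** Section 5.6 plans 44 evaluable of 54 enrolled, so 54 − 44 = 10 (19%), or 5 per arm. The 20% is overall dropout, not loss before Visit 2, so 5 missing per arm is an assumption at the top of a range of 0 to 5.

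**3. Effect on a single result** (two-sided Fisher, clearances per arm, retapamulin v placebo).

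| Available case | p | Missing counted positive | p |
|---|---|---|---|
| 13/22 v 3/22 | 0.004 | 13/27 v 3/27 | 0.006 |
| 11/22 v 3/22 | 0.022 | 11/27 v 3/27 | 0.028 |
| 10/22 v 3/22 | 0.045 | 10/27 v 3/27 | 0.054 |

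The first row is close to the planned 60% v 15%. Only the borderline row crosses 0.05.

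**4. Tipping point for the first row.** Keep 5 missing in each arm and suppose none of the missing retapamulin children cleared.

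- 2 of 5 missing placebo children cleared: 13/27 v 5/27, p=0.042.
- 3 of 5 cleared: 13/27 v 6/27, p=0.086.
- 3 of 5 placebo and 1 of 5 retapamulin cleared: 14/27 v 6/27, p=0.047.

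At the plan's 15% spontaneous rate, 3 or more of 5 clearing has probability 2.7%. Loss is equal in all these cases, yet in the second the difference falls from 59.1% − 13.6% = 45.5 points to 48.1% − 22.2% = 25.9 points. Equal loss is therefore no safeguard.

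**5. How often the conclusion changes.** With exactly 22 of 27 observed per arm, placebo clearance 15%, and all outcomes enumerated, the probability that the available-case test is significant but the missing-as-positive test is not:

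| Retapamulin clearance | Probability |
|---|---|
| 60% | 2.0% |
| 45% | 5.0% |
| 40% | 5.1% |

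No changes occur in the opposite direction in these settings.

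**6. Power if missing-as-positive were made primary.** Exact Fisher, 27 per arm:

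| Loss | Rates analysed | Power |
|---|---|---|
| Exactly 5 per arm | 60% v 15% among 22, analysed over 27 | 0.807 |
| Random, 5/27 | 0.60 × 22/27 = 48.9% v 0.15 × 22/27 = 12.2% | 0.789 |
| Random, 20% | 0.60 × 0.80 = 48% v 0.15 × 0.80 = 12% | 0.775 |

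**The case against.** The exclusion is stated openly, the sample size was built around it, and the stand-alone SAP may contain the missing rules. The consequence is also modest: at the planned effect the conclusion changes in about one trial in fifty, and that takes loss at the top of the assumed range. All of this stands and limits the weight of the point. It does not remove the conflict between the label in 10.3 and 10.4.1 and the rule in 10.5.

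Several stronger readings are tempting but not supported.

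- *There is no rule for missing outcomes.* Exclusion is a rule. What the supplied text lacks is an analysis that keeps all randomized children, and a sensitivity analysis.
- *The primary result is biased, or biased towards retapamulin.* Nothing in the documents shows how loss will relate to outcome.
- *Children who miss Visit 2 without withdrawing are ignored.* Section 10.4.5 provides a follow-up call for them, and the reason given in 10.5, an unrecorded endpoint, fits them too. The loss-to-follow-up definition in 5.7.2 is awkward, since it includes "they have missed all three study visits" and a randomized child has attended Visit 1. That matters only if the three are Visits 1 to 3. The gap is an explicit analysis rule.
- *The wording on evaluability creates a competing analysis set.* Section 6.1.9 is one line under duration of therapy, while 10.3 names the analysis sets. This is a mismatch of terms to tidy up.
- *Withdrawal swabs will be discarded.* Section 10.5 does not say so. A swab inside the Visit 2 window would undercut its stated reason for exclusion, so the text needs only to say that it counts.

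**Conclusion.** The point holds and should be fixed. Followed as written, sections 10.3, 10.4.1 and 10.5 produce an available-case primary result under an ITT label, and the supplied text has no planned check on the children left out. The textual conflict does not depend on any assumption. The size does: it rests on 5 missing per arm, all before Visit 2, and on a two-sided test. With fewer missing, less is at stake. On that basis a result near the planned effect is robust to counting missing as positive, and a borderline result is not. A reader should not infer that the trial is underpowered as planned, or that its result would be wrong; neither follows.

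**What to change.** Replace the last sentence of 10.5 with: *All randomized participants with a Visit 2 culture, or a withdrawal swab (7.3.5) taken within the Visit 2 window, are analysed in their assigned arm regardless of days of ointment used; this primary set is labelled available-case (modified ITT).* Use the same label in 10.3 and 10.4.1.

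Add two pre-specified sensitivity analyses on all randomized participants, including those who miss Visit 2 without withdrawing:

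- (a) a missing Visit 2 culture counted as MRSA-positive;
- (b) a tipping-point analysis varying the number cleared among the missing in each arm.

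Write *all randomized* and not a fixed 54, because 5.6 lets recruitment run until about 54 have completed, so more could be randomized. Make the use of evaluable in 5.6 and 6.1.9 consistent with these sets. If the stand-alone SAP already has such rules, align 10.5 with it.

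The cost is a less favourable label than ITT and a little more analysis work, with no extra children or visits. If the sponsor prefers to make (a) primary and keep the ITT label, the power must be restated: 0.775 to 0.807 at 27 per arm under the losses shown above.
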